5.1.1.1.1. Edoxaban dose recommended for 12 to <18 years old pediatric subjects

Edoxaban treatment will be dispensed to the subject on a monthly visit schedule (see caveat above). The oldest cohort (12 to <18 years old) will receive tablets (15 and/or 30 mg strength, see [Table 5.1](#)). (Doses for all subsequent age cohorts will be by notification to the investigative sites.) Subjects will be instructed to take edoxaban (tablets) orally once a day, at the same time every day, with or without food. Tablets should be swallowed with a glass of water.

Only on Day 5 (+3), the approximately first 12 subjects participating in PK/PD assessment should be fasting one hour prior to intake of edoxaban dose and a maximum of 2 hours after taking edoxaban dose.

Table 5.1: Edoxaban Dose Recommended For All 5 Cohorts (12 to <18 years, 6 to <12 years, 2 to <6 years, 6 months to <2 years, and birth to <6 months)

Age	Body Weight	Dose (Tablet)	Dose (Suspension) (6 mg/mL concentration) ^{c,e}	Dose Reduction ^a
12 to <18 years ^b (At date of consent)	≥60 kg	60 mg QD	NA	45 mg QD
	≥30 and <60 kg	45 mg QD	NA	30 mg QD
	<5th Percentile for Age ^c	30 mg QD	NA	NA
6 to <12 years (At date of consent)	<60 kg Dosed based on mg/kg ^d	NA	1.2 mg/kg with a maximum dose of 45 mg	0.8 mg/kg, with a maximum dose of 45 mg
2 to <6 years (At date of consent)	Dosed based on mg/kg	NA	1.4 mg/kg with a maximum dose of 45 mg	0.7 mg/kg, with a maximum dose of 24 mg
6 months to <2 years (At date of consent)	Dosed based on mg/kg	NA	1.5 mg/kg with a maximum dose of 45 mg	0.75 mg/kg with a maximum dose of 24 mg
>28 days to <6 months (At date of consent)	Dosed based on mg/kg	NA	0.8 mg/kg with a maximum dose of 12 mg/kg	0.4 mg/kg, with a maximum dose of 6 mg/kg
38 weeks gestation to ≤28 days (At date of consent)	Dosed based on mg/kg	NA	To be determined by the IDMC	0.4 ^f mg/kg, with a maximum dose of 6 mg/kg

Abbreviations: eGFR = estimated glomerular filtration rate; IDMC = Independent Data Monitoring Committee; NA = not applicable; P-gp = P-glycoprotein; QD = once a day

^a Conditions for dose reduction:

If a subject requires concomitant administration of P-gp inhibitor (Appendix 17.4.6), the edoxaban dose will be reduced during P-gp administration and re-established to the original dose once P-gp inhibitor administration had concluded.

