Edoxaban dosage regimen will be reduced permanently for subjects with moderate renal impairment for the subject's age and size at randomization as determined by the age appropriate formula: Cockcroft-Gault equation for pediatric subjects ≥12 years of age and modified Schwartz equation for pediatric subjects <12 years of age). Refer to Appendix 17.7 for eGFR values below which dose reduction should be implemented.

If a subject experiences a change in renal function from normal to eGFR ≥30% to ≤50% after randomization, the measurement will be repeated within 1 week to 10 days after correction of the underlying factor's causing pre-azotemia. If the repeat measurement confirms the reduced eGFR, the edoxaban dose reduction will be permanent even if the subject experiences an improvement in the eGFR during the course of the study.

^b Dose reduction due to body weight applies only for fixed doses in subjects 12 to <18 years of age:

If body weight increases or decreases from the categories of weight defined at consent, the subject will be dose adjusted. Subjects who are ≥60 kg of body weight at consent and drop below that body weight will receive 45 mg dose at any subsequent visit. Subjects who are ≥30 and <60 kg at consent and increase their weight to ≥60 kg will increase their dose to 60 mg.

^c Edoxaban dosage regimen will be reduced permanently for subject with body weight <5th percentile for age.
Refer to Appendix 17.9.

^d Edoxaban granulation will be diluted with 8 mL water to provide a concentration of 6 mg/mL dosing suspension. If body weight increases or decreases from the categories of weight defined at consent, the subject will be dose adjusted. Subjects who are \geq 60 kg of body weight at consent and drop below that body weight will receive 45 mg dose at any subsequent visit. Subjects \geq 30 and <60 kg at consent increasing their weight to \geq 60 kg will increase their dose to 60 mg.

Note: Dose is based upon weight at corresponding visit.

^e Edoxaban granules are for subjects <12 years of age only. Subjects 12 to <18 years of age should use crushed edoxaban tablets. For those subjects cannot swallow whole tablets, edoxaban tablets may be crushed and mixed with 2 to 3 ounces of water and immediately administered by mouth or through a gastric tube. The crushed tablets may also be mixed into applesauce and immediately administered..

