5.1.1.2. Edoxaban dose recommended for <12 years old pediatric subjects

Subjects of age <2 years will have dose recommendations based on the PK and safety data from same age cohort in U157 study and subjects evaluated for edoxaban exposure in the previous older cohort in U312 study. The PK and safety data will be reviewed by the IDMC (Section 15.9) who will approve the start of the next younger age cohort. Based on the IDMC review of Cohort 1 data from DU176b-D-U312 and corresponding cohort data from study DU176b-A-U157, the proposed dose that was safe and effective for VTE treatment was 1.2 mg/kg body weight for Cohort 2 (6 to <12 years) (Table 5.1), 1.4 mg/kg body weight for Cohort 3 (2 to <6 years), 1.5 mg/kg, for Cohort 4 (6 months to <2 years), 0.8mg/kg for Cohort 5 (>28 days to <6 months), and will be determined by the IDMC for Cohort 5 (38 weeks gestation to \leq 28 days).

Doses for all subsequent age cohorts will be made by separate notifications to the investigative sites, outside the content of this protocol, and after the IDMC has approved the proposed edoxaban doses. An official notification will be sent when select age cohorts can begin randomization to either SOC or edoxaban treatment. In addition, a notification will indicate that Day 5 PK/PD edoxaban exposure evaluation will no longer be necessary for future subjects randomized to edoxaban in the corresponding age cohort.

Subjects of age <12 years will receive edoxaban granules for oral suspension (60 mg) and will be dosed on an mg/kg basis. Check the body weight prior to dosing and adjust dosage accordingly. Frequency of dosage changing is up to the Investigator's discretion, but the maximum dose would not exceed 45 mg once a day (QD).

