5.2.2. Labeling and Packaging

Investigational products will be provided in adequate quantity for study conduct and labeled in an open-label format. Investigational product labels will include all information required by federal and local regulations.

Edoxaban 15, 30 mg tablets will be supplied by Sponsor in an open-label format. The edoxaban granules for oral suspension 60 mg will be provided in glass bottles, as per visit schedule, for single dose application.

Centrally sourced SOC will be presented in its commercial presentation with clinical study over label. It will include information required by federal and local regulations.

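### Table 5.1 gives conflicting maximum doses for a child under 12 years at 60 kg or more, prints the infant dose caps in mg/kg, and has a footnote heading that obscures who gets the low-weight reduction

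*Combined protocol and SAP*

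**What the plan says.** Table 5.1 is titled as covering all five age cohorts, and the dose-reduction text in the synopsis and Section 5.3.1 sends the reader to it.

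- **6 to <12 years.** The row is labelled <60 kg and gives "1.2 mg/kg with a maximum dose of 45 mg". Its weight cell carries footnote d. That footnote covers subjects of at least 30 but under 60 "kg at consent increasing their weight to" 60 kg or more, and moves them to 60 mg. It also gives a rule for subjects at 60 kg or more "of body weight at consent and drop below that body weight will receive 45 mg dose at any subsequent visit"; footnote b has the same sentence for the tablet cohort.
- **Under 12 years in general.** Section 5.1.1.1.2 lets the investigator decide how often to adjust the dose for weight, but adds that "the maximum dose would not exceed 45 mg once a day (QD").
- **Infants.** The >28 days to <6 months row gives "0.8 mg/kg with a maximum dose of 12 mg/kg" as the full dose and "0.4 mg/kg, with a maximum dose of 6 mg/kg" as the reduced dose. The same 6 mg/kg limit is printed for the ≤28 days row, whose full dose is left to the IDMC. All other suspension caps are in mg (45 or 24 mg).
- **Low body weight.** Footnote b opens: "Dose reduction due to body weight applies only for fixed doses in subjects 12 to <18 years of age". Footnote c, the synopsis, Section 5.1.2 and Section 5.3.1 all provide for a reduction below the 5th weight percentile without an age limit, and Section 5.1.2 says explicitly that the check is for all subjects.

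**The concern.** A dosing table for an anticoagulant in children should give one dose per child, and its maximum should act as a maximum. Table 5.1 falls short in three ways.

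1. A child under 12 who reaches 60 kg is given 60 mg by footnote d and 45 mg by Section 5.1.1.1.2. No row of the table settles which is right.
2. A per-kilogram cap on a per-kilogram dose scales with weight just as the dose does. If it exceeds the dose at one weight, it does so at every weight, and so limits nothing. Granules come as "60 mg will be provided in glass bottles, as per visit schedule, for single dose application", so a bottle holds far more than an infant dose. A fixed cap is a cheap check against a measuring or calculation error.
3. A reader who takes footnote b's heading at face value would withhold the low-weight reduction from a small child under 12, while one following Section 5.1.2 or 5.3.1 would apply it. Section 5.3.1 keeps a weight-based reduction for the rest of the study, so a wrong choice would persist.

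**Working it through.** There is no printed calculation to reproduce. The check sets the stated limits against each other, using dose = min(cap, mg/kg × weight).

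**1. Child under 12 years at 60 kg**

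Inputs: 1.2 mg/kg and the <60 kg label (Table 5.1); 60 mg (footnote d); 45 mg once daily (Section 5.1.1.1.2).

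- Uncapped: 1.2 × 60 = 72 mg, so the maximum decides the dose.
- Section 5.1.1.1.2: 45 mg, or 45/60 = 0.75 mg/kg.
- Footnote d: 60 mg, or 60/60 = 1.0 mg/kg.
- Ratio: 60/45 = 1.33, so footnote d gives 33% more.

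The row ends below 60 kg, so its own 45 mg cap does not reach this child. The contradiction is between footnote d and Section 5.1.1.1.2. Footnote d also addresses subjects already at 60 kg or more at consent, whom its row excludes. That suggests wording carried over from footnote b but does not prove it.

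**2. Infant caps**

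Inputs: 0.8 and 0.4 mg/kg with caps of 12 and 6 mg/kg (Table 5.1). The documents give no infant weights; 2.5 to 10 kg is assumed.

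- Cap divided by dose: 12/0.8 = 15 and 6/0.4 = 15, at every weight.
- Weight above which the printed cap exceeds 45 mg: 45/12 = 3.75 kg (full dose) and 45/6 = 7.5 kg (reduced dose).

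| Weight (kg) | Full dose (mg) | Printed cap (mg) | Reduced dose (mg) | Printed cap (mg) |
|---|---|---|---|---|
| 2.5 | 2.0 | 30 | 1.0 | 15 |
| 5 | 4.0 | 60 | 2.0 | 30 |
| 7.5 | 6.0 | 90 | 3.0 | 45 |
| 10 | 8.0 | 120 | 4.0 | 60 |

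Read as 12 mg and 6 mg, the caps bind at 12/0.8 = 15 kg and 6/0.4 = 15 kg, above the assumed range, so every dose in the table stays the same. The ratio of the two caps (6/12 = 0.50) matches the ratio of the two doses (0.4/0.8 = 0.50), as would be expected if mg was meant.

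**3. Age scope of the <5th-percentile reduction**

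| Points to 12 to <18 years only | Points to all ages |
|---|---|
| Footnote b heading | Section 5.1.2, explicitly all subjects |
| Footnote a lists only P-gp inhibitors and renal impairment | Section 5.3.1, no age limit |
| The only percentile row is in the 12 to <18 block | Synopsis and footnote c, no age limit |

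The left column is the weaker:

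- The text under footnote b's heading deals only with crossing 60 kg and does not mention the percentile.
- Footnote a is not exhaustive: it also omits age ≤28 days, which the synopsis and Section 5.3.1 list as a reason for reduction.
- A separate percentile row is needed where doses are fixed tablets; the mg/kg rows already have a dose-reduction column.

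If the heading were nevertheless followed, a low-weight child would receive 1.2/0.8 = 1.5 times the reduced dose at 6 to <12 years. In the younger rows with a stated full dose the factor would be 2 (1.4/0.7, 1.5/0.75 and 0.8/0.4).

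**The case against.** **Footnote d may be deliberate.** It can be read as the rule for a child who leaves the <60 kg row, with 60 mg matching the tablet dose at 60 kg or more. Rows are fixed by age at consent and participation can last 13 months, so a child who consents at 11 may turn 12 on study, after which the under-12 limit no longer clearly applies. This stands as a reason not to presume that 45 mg is correct. It does not remove the conflict for a child who is still under 12.

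**The infant caps are editorial.** This largely stands. The 0.8 and 0.4 mg/kg doses are clear, and corrected caps would not bind at plausible infant weights. A reader might infer that the table permits a 15-fold overdose. It does not: the cap is a ceiling that limits nothing, and no instruction tells anyone to give 12 mg/kg.

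**The low-weight rule is not really open.** This also stands in large part. A reader might infer that the intent cannot be determined and that every low-weight child under 12 has two equally supported doses. Four places set no age limit, and the contrary points are weak. What is left is a misleading heading and an incomplete footnote.

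**Doses for younger cohorts reach sites by separate notification.** True, and those notifications are not in the documents, so whether any site met a conflict is unknown. They do not repair the protocol text.

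**Conclusion.** The point holds as two dose-limit errors and one unclear heading.

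- The 60 mg versus 45 mg conflict is direct and matters most: a 33% difference at 60 kg. The documents do not say how many children under 12 reach that weight.
- The infant caps are wrong as printed, and a unit slip is the probable cause. The practical effect is the loss of a backstop, with no change to any correctly calculated dose. That conclusion rests on infants weighing less than 15 kg.
- Footnote b's heading conflicts with the rest of the protocol, whose weight favours applying the <5th-percentile reduction at all ages.

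A reader might also infer an error in the 45 mg cap shared by the full and reduced doses at 6 to <12 years. The reduction does shrink above 45/1.2 = 37.5 kg and vanish at 45/0.8 = 56.25 kg, but nothing in the documents shows that this is unintended. It is at most a question to the sponsor.

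None of this bears on sample size, power, endpoints or analysis.

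**What to change.** 1. **Child under 12 years at 60 kg or more.** The sponsor should state one dose. If it is 45 mg, delete the 60 mg sentence from footnote d. If it is 60 mg, amend the 45 mg limit in Section 5.1.1.1.2 and add a row for this weight. Either way, remove or reword the footnote d sentence about subjects already at 60 kg or more at consent, to fit the rows that result.
2. **Infant caps.** After sponsor and IDMC confirmation, restate them as 12 mg (one place) and 6 mg (two places).
3. **Low-weight reduction.** Limit footnote b's heading to the 30 and 60 kg weight categories, and add the <5th-percentile condition to footnote a. If the sponsor instead confirms that 12 to <18 years only is intended, put that limit into footnote c, the synopsis, Section 5.1.2 and Section 5.3.1. Settle this together with item 1, because footnote d applies the same weight categories at 6 to <12 years.
4. **Site notifications.** Check that those already issued match the corrected table.

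The cost is a text amendment to one table, its footnotes and the matching dosing text, plus the notification check. Design, sample size and analysis stay as they are.

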Edoxaban will be started orally at the age/weight/renal function appropriate dose (see Section 5.1.1.1.1) for the Treatment Period (see Section 5.2.4.1). The following dosage forms will be provided for this study:

- Edoxaban 15 mg and 30 mg tablets for 12 to <18 years old subjects;
 - 60 mg dose will be dispensed with two 30 mg tablets
 - 45 mg dose will be dispensed with one 30 mg tablet plus one 15 mg tablet
 - 30 mg dose will be dispensed with one 30 mg tablet
- If a subject does not have the capacity to swallow tablets in the 12 to <18 year old group, the tablets may be crushed and served with applesauce or mixed with 2 to 3 ounces of water and immediately administered by mouth or through a gastric tube.
- Edoxaban granules for oral suspension 60 mg. It will be reconstituted in 8 mL water to provide a 6 mg/mL liquid suspension for subjects younger than 12 years old. Doses provided by the granulation formulation

will be dispensed with an oral dosing syringe according to the recommended doses for the age cohort.

All subjects will receive once a day edoxaban tablet(s) of 15 mg and/or 30 mg strength if they are at least 12 years of age. Subjects younger than 12 years of age will receive edoxaban granules for oral suspension. In each cohort, doses will be selected to elicit target exposures comparable to those achieved from adult doses of 60 mg if no dose adjustment needed.

Dosing regimen for each age cohort will be determined from Phase 1 single dose Study U157 and population based PK.

The dose for the 12 to <18 years of age cohort was selected from the Study DU176b-A-U157 data that were available when this Study U312 was first designed (see Section 5.1.1.1.1).

Based on subsequent IDMC review of Cohort 1 (12 to <18 years of age) data from this Study U312 and corresponding cohort data from Study U157, the proposed dose for 6 to <12 years and 2 to < 6 years cohort is proposed; for subjects < 2 years, the final dose for the cohort is based upon IDMC recommendation (see Section 5.1.1.1.2).

Subjects will be instructed to take edoxaban (tablets or granules) orally once a day, at the same time every day, with or without food. Tablets should be swallowed with a glass of water.

Edoxaban dosage regimen will be reduced (see Table 5.1) the following reasons:

Body Weight (BW) <5th percentile of subject's age (see Appendix 17.9)

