- The edoxaban dosage regimen will be reduced permanently for subjects with moderate renal impairment (eGFR) $\geq 30\%$ to $\leq 50\%$ of normal for the subject's age and size at randomization as determined by the age-appropriate formula: Cockcroft-Gault equation for pediatric subjects ≥ 12 years of age and modified Schwartz equation for pediatric subjects <12 years of age (Appendix 17.7). If a subject experiences a change in renal function from normal to eGFR $\geq 30\%$ to $\leq 50\%$ after randomization, the measurement will be repeated within 1 week to 10 days after correction of the underlying factor's causing pre-azotemia. If the repeat measurement confirms the reduced eGFR, the edoxaban dose will be reduced permanently.

- Additionally, if a subject requires concomitant administration of a certain P-glycoprotein (P-gp) inhibitor (Appendix 17.4.6), the edoxaban dose will be reduced during P-gp administration and re-established to the original dose once P-gp inhibitor administration had concluded.
- Subject is ≤ 28 days old (corrected for gestation age of 38 weeks). This may change based on the IDMC recommendation.

Randomization to Standard of Care Treatment Arm

Standard of care treatment will be dispensed to the subject on a monthly visit schedule. After Month 3, on a case-by-case basis, confirmed by the Sponsor, a 3-month dispense may occur to facilitate subject travel arrangements.

Local SOC sourcing:

The SOC will be provided by the Investigator. Subject will be treated with LMWH, VKA, or SP Xa inhibitors according to the site SOC treatment regimen (see Section 5.1.1.2).

Central/Sponsor Sourcing:

However, if there are regulatory or site hurdles providing the SOC, the Sponsor will provide SOC as enoxaparin or fondaparinux or warfarin as follows:

- Enoxaparin – Subjects will be treated with enoxaparin alone or can be switched to warfarin anytime during the study treatment period.
 - Enoxaparin (LMWH) will be provided to the subjects as solution for subcutaneous (SC) injection in pre-filled syringes with 60 mg/0.6 mL, 80 mg/0.8 mL, and 100 mg/1.0 mL concentration for injection, or as multiple dose vials (for subjects < 10 kg) for injection where allowed per standard clinical practice.
- Fondaparinux – Subjects will be treated with fondaparinux alone or can be switched to warfarin anytime during the study treatment period.

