5.1.2. Method of Treatment Allocation

Eligible subjects will be stratified by

1. Age (12 to <18 years of age; 6 to <12 years of age; 2 to <6 years of age; 6 months of age to <2 years of age; birth to <6 months of age)
2. Regions (ie US/Canada, Europe, Asia/Pacific and Rest of the World). Additional regions may be included if needed)

An independent biostatistician will generate the randomization schedule in accordance with the operating procedure for allocating study drug.

At randomization, the Investigator provides the IXRS with the study center number; the subject's presenting diagnosis (symptomatic VTE) and date of birth. Dose reduction stratification will take into account for:

- eGFR is 30-50% of normal for age and size (Appendix 17.7).
- Whether the subject is receiving concomitant treatment with P-gp inhibitors (Appendix 17.4.6).
- For all subject: whether body weight $<5^{\text{th}}$ percentile of subject's age (see Appendix 17.9).

The IXRS will assign the unique subject identification number, allocate the treatment group assignment for the subject and provide the appropriate drug supply kit number(s), for edoxaban and centrally sourced SOC.

A fax or e-mail will be sent by the IXRS to provide the appropriate drug supply kit number(s). The fax or e-mail will also provide a calendar with dates of subsequent prescheduled visits and drug resupply.

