5.3.1. Edoxaban Dose Reduction

During the treatment period, a subject may reduce the dose of edoxaban for any of the following reasons ([Table 5.1](#)):

- eGFR is 30-50% of normal for age and size ([Appendix 17.7](#)).
- Subject is receiving concomitant treatment with P-gp inhibitors.
- Body weight <5th percentile of subject's age (see [Appendix 17.9](#)).
- Subject is \leq 28 days old (corrected for gestation age of 38 weeks). This may change based on the IDMC recommendation.

For subjects receiving P-gp inhibitors, the dose of edoxaban will only be reduced during the administration of the concomitant P-gp inhibitor. Subjects experiencing eGFR or body weight reduction will maintain their reduced edoxaban dose for the duration of the study. Once the subject turns $>$ 28 days old, the dose may be increased to 0.8 mg/kg.

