17.9. Growth Chart (2 to 20 years and Birth to 24 Months)

Published May 30, 2000 (modified 11/21/00).

SOURCE: Developed by the National Center for Health Statistics in collaboration with the National Center for Chronic Disease Prevention and Health Promotion (2000) <http://www.cdc.gov/growthcharts>

[figure not shown]
SAFER • HEALTHIER • PEOPLE™

2 to 20 years: Girls

Stature-for-age and Weight-for-age percentiles

NAME _____

RECORD # _____

[figure not shown]

[figure not shown]
Published May 30, 2000 (modified 11/21/00).

SOURCE: Developed by the National Center for Health Statistics in collaboration with the National Center for Chronic Disease Prevention and Health Promotion (2000).
<http://www.cdc.gov/growthcharts>

SAFER • HEALTHIER • PEOPLE™

Published by the Centers for Disease Control and Prevention, November 1, 2009
SOURCE: WHO Child Growth Standards (<http://www.who.int/childgrowth/en>)

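### Table 5.1 footnote d raises the dose to 60 mg on a row capped at 45 mg, and the protocol conflicts with itself on whether low weight reduces the dose under 12 years

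*Combined protocol and SAP*

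**What the plan says.** Table 5.1 (Section 5.1.1.1.1) covers all five cohorts and assigns rows by age at consent.

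**Dose cap under 12 years**
- The 6 to <12 year row is limited to body weight below 60 kg. It gives 1.2 mg/kg of suspension, capped at 45 mg.
- Footnote d is attached to that row. After the reconstitution instruction it adds two weight rules. A child at 60 kg or more at consent who falls below 60 kg moves to 45 mg. A child between 30 and 60 kg at consent who reaches 60 kg moves to 60 mg.
- The section on doses for subjects under 12 years (printed as 5.1.1.2, after the table notes) sets a once-daily maximum of 45 mg for all of them.

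**Reduction for low weight**
- Footnote b: "Dose reduction due to body weight applies only for fixed doses in subjects 12 to <18 years of age".
- The percentile row, "<5th Percentile for Age", appears only in the 12 to <18 year block. It gives 30 mg and has no entry under Dose Reduction.
- Footnote a, marked on the Dose Reduction column, names two conditions: P-gp inhibitors and renal impairment.
- The synopsis lists "Body Weight (BW) <5th percentile of" the subject's age as a reason for reduction and refers to Table 5.1. The same list includes subjects up to "28 days old (corrected for gestation age of 38 weeks").
- Section 5.1.2, on inputs to the randomization system: "For all subject: whether body weight" is below the 5th percentile.
- Section 5.3.1 repeats "Body weight <5th percentile of" the subject's age, again with a reference to Table 5.1.

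**The concern.** A site dosing a child aged 6 to <12 years who reaches 60 kg cannot obey both footnote d and the 45 mg cap. A site dosing a child under 12 below the 5th percentile finds one text that rules a weight-based reduction out and three that list it without an age limit. The drug is an anticoagulant, so too much risks bleeding and too little risks recurrent thrombosis. The choice also lasts, since Section 5.3.1 says: "Subjects experiencing eGFR or body weight reduction will maintain their reduced edoxaban dose for the duration of the study".

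**Working it through.** **Part 1: footnote d against the cap**

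Inputs from Table 5.1: 1.2 mg/kg and a 45 mg cap (6 to <12 year row); 60 mg at 60 kg or more (footnote d). The under-12 section repeats the 45 mg cap.

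- Weight at which the row's dose meets its cap: 45 / 1.2 = 37.5 kg.
- Dose at 60 kg under the row: 1.2 x 60 = 72 mg, capped at 45 mg, which is 45 / 60 = 0.75 mg/kg.
- Dose at 60 kg under footnote d: 60 mg, which is 60 / 60 = 1.0 mg/kg.
- Ratio: 60 / 45 = 1.33, a third above the stated maximum.

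From 37.5 kg upwards the row's dose is fixed at 45 mg, so 60 mg cannot be reached under the cap. Two statements set 45 mg and one sets 60 mg. Footnote d's weight rules nearly repeat footnote b's rules for switching between adolescent tablet doses, where 60 mg is the correct dose at 60 kg or more. That points to copied text. Footnote d's first rule has the same problem as its second: moving to 45 mg on falling below 60 kg implies a higher dose above it.

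**Part 2: low weight under 12 years**

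| Text | Scope of low-weight reduction |
|---|---|
| Footnote b | 12 to <18 years only |
| Table 5.1 rows | percentile row at 12 to <18 years only |
| Footnote a | weight not listed as a condition |
| Section 5.1.2 | all subjects |
| Synopsis; Section 5.3.1 | no age limit, both referring to Table 5.1 |
| Footnote c | no age limit in its wording |

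Footnote c's marker is on the adolescent percentile row and, as printed, also on the suspension column header. Suspension is only for children under 12, so taken literally the second marker favours an all-ages rule. It may instead be a slip for d, because footnote d explains the 6 mg/mL concentration named in that header.

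Table 5.1 gives no percentile dose under 12. *If* a low-weight child were given the Dose Reduction column dose, which is an assumption, full dose over reduced dose would be:
- 6 to <12 years: 1.2 / 0.8 = 1.5
- 2 to <6 years: 1.4 / 0.7 = 2.0
- 6 months to <2 years: 1.5 / 0.75 = 2.0
- >28 days to <6 months: 0.8 / 0.4 = 2.0

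For example, at an assumed 20 kg in the 6 to <12 year row: 20 x 1.2 = 24 mg against 20 x 0.8 = 16 mg.

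Number of children: the planned Day 5 PK subset of Cohorts 2 to 4 alone is 3 x 12 = 36. The edoxaban arm less the 12 adolescent PK subjects is 137 - 12 = 125. The documents do not give the share below the 5th percentile. At an assumed 5%, 0.05 x 36 = 1.8 and 0.05 x 125 = 6.25, so about 2 to 6 children. Doubling the share doubles the count, to 3.6 and 12.5.

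**The case against.** **On footnote d.** The row is limited to children below 60 kg, which suggests that someone had a separate rule for heavier children in mind, and 60 mg is what an adolescent of that weight receives. So 60 mg could be deliberate. This cannot be excluded, and the fix allows for it. But a reader who inferred that the two texts are equally likely to be wrong would go too far: the row and the under-12 section both give 45 mg, and the footnote resembles copied text.

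**On low weight.** The best defence is that the table governs. The synopsis and Section 5.3.1 refer to it, footnote a leaves weight out, doses per kilogram already scale with weight, and Section 5.1.2 lists system inputs rather than doses. Most of this stands, and it is why the table leans towards adolescents only. It does not settle the matter. Section 5.1.2 says all subjects outright, and the synopsis and Section 5.3.1 lists also name neonates, so they are not adolescent lists. Footnote b could also be read as introducing only the tablet-band switches that follow it. Appendix 17.9, "Growth Chart (2 to 20 years and Birth to 24 Months"), includes an infant chart, but standard charts in an appendix do not create a dosing rule.

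A reader might infer that footnote b is the error and the reduction is meant at every age. The documents do not support that; they leave the question open.

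**Conclusion.** This is an internal inconsistency in dosing that should be fixed. Footnote d is wrong as written: followed literally, it exceeds a stated maximum by a third. That holds without any assumption, though it concerns only children aged 6 to <12 years at 60 kg or more, who will be few. The low-weight conflict is real but unresolved, with the table leaning towards adolescents only. Its 1.5-fold and 2-fold gaps rest on the assumption that the Dose Reduction column would be used, and the count of about 2 to 6 rests on an assumed 5% share.

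A reader might infer that children are being misdosed, or that the protocol itself prescribes two doses differing by up to 2-fold for low-weight children. Neither is supported. Doses for the younger cohorts also go out in separate notices that are not in the documents, and no percentile dose is stated under 12. Nothing here bears on the 68-event target, the sample size or the primary analysis.

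**What to change.** **Footnote d.** Delete both 60 kg band-switch sentences, not only the one that gives 60 mg. Keep the reconstitution text and the note that the dose follows weight at each visit. Remove the 60 kg limit from the row, so that the 45 mg cap governs every subject under 12. If the sponsor confirms that 60 mg is intended, amend the row's cap and the under-12 section instead.

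**Low weight.** The sponsor and the data monitoring committee should state, cohort by cohort, whether the 5th-percentile reduction applies under 12.
- If it does not, restrict the synopsis, Sections 5.1.2 and 5.3.1 and the randomization-system logic to 12 to <18 years.
- If it does, limit footnote b to the tablet-band switches, and add the percentile condition and an explicit dose to footnote a and the rows under 12.
- In either case, correct or confirm footnote c's marker on the suspension header.

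The cost is amendment wording plus a check of the randomization system, site notices and dosing cards. No extra patients are needed.
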